### 3.2 Objectives and Endpoints - Part B (PUPs/MTPs)

Objectives	Endpoints
Primary Efficacy	

 
Assess the efficacy of KOVALTRY within 48 hours of previous prophylaxis infusion in previously untreated/minimally treated Chinese children (<6 years of age) with severe hemophilia A
 
	
 
ABR within 48 hours of previous prophylaxis infusion
 

Secondary Efficacy	

 
Evaluate the efficacy of prophylaxis treatment with KOVALTRY
 
Assess the efficacy of KOVALTRY for treatment of bleeding episodes
 
Evaluate the in vivo recovery of KOVALTRY
 
Hemostatic control for minor surgeries
 
	
 
ABR during the prophylaxis period
 
Number of infusions required to treat a bleed and response to treatment of bleeds
 
In vivo recovery of KOVALTRY at baseline and study end
 
Physician assessment of adequacy of hemostasis in minor surgery
 

Safety	

 
Assess the safety of KOVALTRY for prophylaxis and treatment of bleeding episodes in previously untreated/minimally treated Chinese children (<6 years of age) with severe hemophilia A
 
	
 
FVIII inhibitor development by the Nijmegen Bethesda assay
 
Treatment-emergent adverse events (TEAEs)
 

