#### 4.1.2 Part B (PUPs/MTPs)

Part B will assess the efficacy and safety of KOVALTRY in previously untreated/minimally treated Chinese children with severe hemophilia A. Part B will investigate approximately 6 PUPs/MTPs. Efficacy and safety assessments are outlined in the SoA in Section 1.3.2.

Efficacy and safety data for the use of KOVALTRY for treatment of bleeding episodes will also be collected.

- Study participants will be treated until at least 50 ED is achieved.
  - Treatment may begin with start of prophylaxis with 15 to 50 IU/kg (minimum dose: 250 IU) at least 1 day a week; alternatively, prophylaxis

can be started directly with a once-a-week schedule minimum dose of 250 IU for PUPs/MTPs of any weight.

- The starting dose may be tailored to the participant's weight or demonstrated bleeding tendency.
- Individual participant dose decisions are at the discretion of the investigator.
- Part B will include 8 study visits (Screening, Baseline, Visit 3 [approximately 5 ED], Visit 4 [approximately 10 ED], Visit 5 [approximately 15 ED], Visit 6 [approximately 20 ED], Visit 7/Interim visit [approximately 30 to 40 ED], and Visit 8/Final visit [50 ED]/Early Termination). All parents/caregivers of participants in Part B will receive a safety follow-up call approximately 2 weeks after the end of treatment.

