#### 4.4 End of Study Definition

A participant is considered to have completed the study if he has completed the last study visit, as shown in the Schedule of Activities for Part A (Section 1.3.1) or Part B (Section 1.3.2), or optional ITI treatment (Section 10.5.2).

Completion of Part A is when the last participant in Part A completes the final visit or early termination as shown in the Schedule of Activities for Part A (Section 1.3.1).

Completion of Part B is when the last participant in Part B completes the final visit or early termination as shown in the Schedule of Activities for Part B (Section 1.3.2).

Study participants who develop high-titer FVIII inhibitor and decide to enter optional ITI treatment with study intervention will discontinue participation in either Part A or Part B and complete the Early Termination visit. The end of study for these participants is defined as completion of the Optional ITI Treatment (Section 10.5.1).

Study participants who develop high titer FVIII inhibitor and decide to receive ITI with another product outside of the study will complete the Early Termination visit and leave the study.

The study itself will be considered complete after the last visit of the last participant for all centers has occurred.

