## **6.8 Discontinuation of Study Intervention and Participant Discontinuation/Withdrawal**

### **6.8.1 Discontinuation of Study Intervention**

In rare instances, it may be necessary for a participant to permanently discontinue study intervention. If study intervention is permanently discontinued, the participant will not remain in the study, but will be evaluated for safety at his last study visit. Unscheduled visits are permitted at any time at the discretion of the investigator.

See the SoAs (Section [1.3.1](#) for Part A and Section [1.3.2](#) for Part B) for data to be collected at the time of intervention discontinuation and for any further evaluations that need to be completed. For cases of early termination in Part A, all investigations for Visit 5 should be performed. For cases of early termination in Part B, all investigations for Visit 8/Final visit should be performed.

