### **6.8.3 Participant Discontinuation/Withdrawal from the Study**

A participant who withdraws is one who discontinues from a clinical study for any reason. The participant will not suffer any disadvantage as a result.

A participant may be withdrawn from the study at any time:

- At their own request or at the request of their parent/legal representative. Without giving reasons, a participant may decline to participate further.
- At the discretion of the investigator for safety, behavioral, compliance, or administrative reasons.

A participant must be withdrawn from the study:

- In case of positive inhibitor result at Screening or in case of high titer inhibitor result at the Baseline visit.
- In case of development of a high-titer inhibitor related to the study drug (>5 BU/mL, confirmed on a second measurement done in central laboratory [Part A] or in local laboratory [Part B] within 2 weeks of notification of initial detection of high-titer inhibitor) that interferes with effective treatment with FVIII and the investigator believes that it is in the best interest of the participant to receive treatment for management with ITI outside of the study. There is the option to receive ITI with study drug. In this case, the participant discontinues participation in Part A or Part B and continues in the Optional ITI Treatment. ITI with study drug will be provided at a dose of up to 200 IU/kg daily for up to a maximum of 18 months (see Section 10.5.1 for additional information). While awaiting confirmatory testing for the initial result, treatment will be at the investigator's discretion according to local standard of care.
- If he fails to comply with scheduled appointments for the study-related evaluations and with EPD data entry to an extent that compromises collection of critical data.

If the participant withdraws consent for disclosure of future information, the Sponsor may retain and continue to use any data collected before such a withdrawal of consent.

At the time of discontinuing from the study, any attempts should be taken to conduct an early discontinuation visit (Visit 5 for Part A or Visit 8/Final visit for Part B). See the SoAs (Section 1.3.1 for Part A and Section 1.3.2 for Part B) for data to be collected at the time of study discontinuation and follow-up and for any further evaluations that need to be completed.

The reason for each withdrawal must be recorded in the CRF and in participant's medical record.

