### 7.3.2 Incremental Recovery of KOVALTRY

Incremental recovery will be determined by collecting a sample for KOVALTRY level before the scheduled infusion, and a second sample collected 15 to 30 min after end of the infusion.

Blood samples for KOVALTRY trough (predose) and recovery levels (15 to 30 min post infusion) will be collected in all participants at Visits 2, 4, and 5 in Part A; at Visits 2, 6, and 8 in Part B; and at additional time points based on the investigator's discretion. Infusions must be given in hospital and use the participants assigned treatment dose, rounded to full vial size.

The exact times for infusion and blood sampling before and after infusion and the dose administered will be documented in the CRF.

Infusions given at study visits will be recorded in the site participant records, which will be the source documents and will be used to enter this information in the CRF.

The samples will be collected as described in detail in the laboratory manual. All samples will be processed in the central laboratory (Part A) or local laboratory (Part B). Plasma concentrations of FVIII will be measured using a validated FVIII activity assay ("chromogenic assay" for Part A, "one-stage clotting assay" for Part B).

Samples for incremental recovery should be collected on days when the next prophylactic infusion is scheduled and at least 48 h after the last infusion prior to this. The measurements should only be performed when the participant is not actively bleeding and when FVIII:C levels are close to trough.

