## Statistical Analysis Plan

BAY 81-8973 (KOVALTRY) / 19855

Page: 12 of 15

Factor VIII concentration values and recovery values will be summarized by time point.

$$\text{recovery} = (\text{post-infusion FVIII} - \text{pre-infusion FVIII}) * \text{weight / dose (in IU)}$$

If a Factor VIII concentration value is below the LLOQ (lower limit of quantification), a data point will be substituted by one half of this limit.

A validity flag for recovery values and their corresponding pre- and post-infusion FVIII values will be created. These values will be considered valid except when any of the following conditions apply:

- If pre-infusion FVIII  $\geq$  post-infusion FVIII [biologically impossible in the absence of inhibitors]
- If pre-infusion FVIII  $> 40$  IU/dl (note 1 IU/dl=1%) [protocol violation]
- If post-infusion FVIII  $< 10$  IU/dl (note 1 IU/dl=1%) [biologically impossible in the absence of inhibitors]

In the tables displaying descriptive statistics of recovery values, if a recovery is flagged as not valid, then the corresponding pre-infusion FVIII, post-infusion FVIII, and recovery values will not be included.

Furthermore, if there are multiple FVIII values for a subject and timepoint, only the record with the lowest LLOQ will be used. The others values will be excluded from the analysis dataset.

Besides the efficacy variables will be analyzed in summary statistics by age group (<12 or  $\geq$ 12 years of age), if it is applicable, the efficacy endpoints of ABR will also be estimated by a negative binomial regression with duration of treatment period as offset variable.

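### The recovery validity rule in SAP 6.2.2 does not look at inhibitor status, so the Part B recovery table describes neither all participants nor the inhibitor-free ones

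*SAP*

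**What the plan says.** SAP 6.2.2 computes recovery as the rise in FVIII times weight divided by dose, and sets a validity flag. Any one of three conditions makes a recovery not valid: pre-infusion FVIII at or above post-infusion FVIII, pre-infusion FVIII above 40 IU/dL, or post-infusion FVIII below 10 IU/dL. The first and third carry the bracketed reason "biologically impossible in the absence of inhibitors". The second is labelled a protocol violation. In the descriptive tables, "if a recovery is flagged as not valid, then the corresponding pre-infusion FVIII, post-infusion FVIII, and recovery values will not be included".

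The Part B endpoint is "In vivo recovery of KOVALTRY at baseline and study end" (Protocol 3.2). Samples are due "at Visits 2, 6, and 8 in Part B" (Protocol 7.3.2), using each child's assigned dose. Participants who develop a high-titer inhibitor and choose immune tolerance induction (ITI) with study drug "will discontinue participation in either Part A or Part B and complete the Early Termination visit" (Protocol 4.4). Protocol 6.8.1 adds: "For cases of early termination in Part B, all investigations for Visit 8/Final visit should be performed". Those investigations include recovery (Protocol 7.2.8). Protocol 6.8.3 is softer: "any attempts should be taken to conduct an early discontinuation visit".

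SAP 3.1.2 and Protocol 9.2.2 assume that 35% to 54% of Part B participants develop an inhibitor. SAP 6.2 bases all efficacy analyses on the mITT population.

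**The concern.** An inhibitor neutralises infused FVIII, so a very low or absent rise is a genuine result in an inhibitor case. The SAP's own bracket concedes this, but the operative condition is numeric only. A programmer following the text would remove a child with a strong inhibitor and keep a child with a weak one.

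The rule also applies to Part A, but Protocol 2.3.1 puts the inhibitor risk in previously treated patients below 1%. Part B is where it matters.

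At stake is what the study-end recovery table means. Its mean and minimum would not describe all mITT participants with a sample, because genuine low values are gone. Nor would they describe recovery without inhibitors, because inhibitor cases above the cut-offs remain. The SAP plans no recovery summary by inhibitor status.

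**Working it through.** **1. The plan's own figure.** The SAP states at least 92% probability of seeing one or more inhibitor cases among 6. With 1 − (1 − p)^6, p = 0.35 gives 0.925 and p = 0.54 gives 0.991, so the figure reproduces. Expected cases are 6 × 0.35 = 2.1 to 6 × 0.54 = 3.2, including low-titer cases.

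**2. What the 10 IU/dL cut-off means as a recovery.** Protocol 4.1.2 allows "prophylaxis with 15 to 50 IU/kg (minimum dose: 250 IU) at least 1 day a week". With pre-infusion FVIII near 0, the cut-off is 10 / dose per kg:
- 15 IU/kg: 10/15 = 0.67. This dose meets the 250 IU minimum only from 250/15 = 16.7 kg.
- 25 IU/kg (250 IU in a 10 kg child): 10/25 = 0.40.
- 50 IU/kg: 10/50 = 0.20.

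The same degree of inhibition can therefore be dropped at one dose and kept at another. For comparison, the package insert (Table 19) gives a median recovery of 1.6 at study start in previously treated children aged 0 to <6 years. At that recovery the post-infusion level would be 1.6 × 15 = 24 to 1.6 × 50 = 80 IU/dL, well above 10. The cut-off would thus mainly catch inhibitor cases or sample errors.

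**3. Effect on the mean over all sampled participants (illustration).** Let n be the number sampled, k the number dropped, r the unaffected recovery and a the recovery of a dropped case.

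Ratio of reported to all-participant mean = n·r / [(n − k)·r + k·a].

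Assumptions: r = 1.4 to 2.0 (Table 19 quartiles after 6 months, same age group); a from 0 to the cut-off, with pre ≥ post counted as 0; all six sampled; all unaffected values equal. The Table 19 values are from the chromogenic assay in previously treated children. Part B uses the one-stage assay, so they are only a proxy.

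| Cut-off | k = 1 | k = 2 |
|---|---|---|
| 0.67 | 1.10 to 1.20 | 1.21 to 1.50 |
| 0.40 | 1.14 to 1.20 | 1.31 to 1.50 |

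Lowest entry: 6 × 1.4 / (5 × 1.4 + 0.667) = 8.4/7.667 = 1.10. Highest for k = 1: 6r/5r = 1.20. With only five sampled and cut-off 0.67, k = 1 gives 1.12 to 1.25.

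**4. Effect against inhibitor-free recovery.** Take four unaffected children at 1.6, one inhibitor case at 0.1 (dropped) and one at 0.8 (kept); these values are assumed.
- All six: (6.4 + 0.1 + 0.8)/6 = 1.22.
- Under the rule: (6.4 + 0.8)/5 = 1.44.
- Inhibitor-free: 1.60.

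The reported mean is 18% above the first target and 10% below the second (1.44/1.60 = 0.90).

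**5. How often.** The documents do not give the share of inhibitor cases that would fall below the cut-offs. If it were a quarter, the chance that at least one of six is dropped is 1 − (1 − 0.25p)^6 = 42% to 58% for p = 0.35 to 0.54. If it were half, it is 68% to 85%. Both shares are assumptions, and both calculations suppose that every child has a sample.

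**The case against.** **Intent and unseen specifications.** The bracket shows that the authors had inhibitors in mind. SAP 1 makes separate dataset and table specifications part of the plan, and they may carry an exception. That is possible, but the SAP text as it stands has none, and either reading needs a clarifying sentence.

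**Fewer affected samples than the inhibitor rate suggests.** A reader might infer that 35% to 54% of study-end recoveries would be discarded. The documents do not support that. The rate includes low-titer cases, which may stay above the cut-offs. Protocol 7.3.2 asks for samples at least 48 hours after the last infusion and only when the child is not actively bleeding. A high-titer case that leaves for ITI before Visit 6 gives no Visit 6 value, and Protocol 6.8.3 asks only for attempts at the early visit. This stands, and it is why no size can be fixed.

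**Direction.** A reader might also infer that the rule always inflates reported recovery. Step 4 shows that this depends on the target: relative to inhibitor-free participants the mean can be too low.

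**Other reporting.** All data are listed, and the numbers of available and missing values are shown (SAP 4.1 and 6). Inhibitors are summarised by time point (SAP 6.4.3). A first positive test triggers its own recovery check (Protocol 8.10.2), and recovery is listed for ITI participants (Protocol 9.4.4). With about 6 children, a reader could link recovery to titer by hand. This limits the harm, but it does not correct the summary statistics or give the reason for an exclusion.

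**Conclusion.** The concern holds for the SAP text. Two of the three validity conditions remove genuine low recoveries in inhibitor cases, for a reason that does not apply to them, and the resulting table has no defined population. Against the mean over all sampled mITT participants, dropping such a case overstates recovery, provided only that its value lies below the mean of those kept. Against inhibitor-free recovery, a retained inhibitor case can pull the mean down.

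The size is illustrative: about 1.1- to 1.2-fold for one dropped case among six, under the assumptions in step 3. Larger ratios need more dropped cases and should carry little weight. The median is less sensitive but not immune. With recoveries of 1.4, 1.6, 1.8 and 2.0 plus two dropped values near 0, it is 1.5 over all six and 1.7 under the rule, while the mean goes from 6.8/6 = 1.13 to 6.8/4 = 1.70.

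The consequence is modest. This is one descriptive secondary endpoint in about 6 children, no hypothesis is tested, and the values stay in listings. The point does not touch the primary ABR or suggest that the trial's efficacy result as a whole is inflated.

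**What to change.** Amend SAP 6.2.2 as follows.

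- Apply the pre ≥ post and post <10 IU/dL exclusions only when the participant has no confirmed inhibitor. Confirmed means ≥0.6 BU/mL in two samples, with the first positive sample on or before that recovery visit and no later negative result before it.
- Treat a recovery taken at the first exposure of a previously untreated patient (PUP) as inhibitor-negative, since no test is planned before treatment (Protocol 8.10.2). For PUPs whose recovery is taken when prophylaxis starts after on-demand exposures (Protocol 6.6.2 and 7.2.2), use the latest available inhibitor result.
- For a confirmed inhibitor case with pre ≥ post, first query for swapped or mislabelled samples. If the values are verified, keep them.
- Leave the pre-infusion >40 IU/dL condition unchanged.
- Present recovery for all mITT participants with a sample and for those without a confirmed inhibitor, with the number flagged and the reason at each time point.

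The 10 IU/dL cut-off stays dose-dependent for participants still subject to it. This should matter little: even at the Table 19 lower quartile of 1.3 at study start, 15 IU/kg gives 1.3 × 15 = 19.5 IU/dL.

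The cost is a few sentences, one merge with the inhibitor results and one extra table split. No new sampling is needed. Mean recovery over all participants may look less favourable.

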### 6.3 Pharmacokinetics/pharmacodynamics

Pharmacokinetic analysis will be only applied for Part A.

The concentration-times courses of FVIII will be tabulated by age groups (<12 or  $\geq$ 12 years of age; pediatric subgroup of <6y and 6 to <12y; and subgroup of 12-<18y and  $\geq$ 18y if applicable) for the planned sampling points. The following statistics will be calculated for each of the sampling points (if appropriate): geometric mean, geometric standard deviation (re-transformed standard deviation of the logarithms) and coefficient of variation, arithmetic mean, standard deviation and coefficient of variation, minimum, median, maximum value, and the number of measurements. Geometric means at any time will only be calculated if at least 2/3 of the individual data were measured and were above the lower limit of quantification (LLOQ). For the calculation of the mean value a data point below LLOQ will be substituted by one half of this limit. In tables showing mean values, where values below LLOQ are included in the calculation of mean values, these means will be marked.

Individual and mean (if appropriate) concentration vs time profiles (using the actual sampling times for individual plots and the planned sampling times for mean plots) will be plotted by

## Statistical Analysis Plan

BAY 81-8973 (KOVALTRY) / 19855

Page: 13 of 15

age group (<12 or  $\geq$ 12 years of age; pediatric subgroup of <6y and 6 to <12y; and subgroup of 12-<18y and  $\geq$ 18y if applicable) using both linear and semilogarithmic scale.

Pharmacokinetic parameters will be summarized by the statistics mentioned above for each age group (<12 or  $\geq$ 12 years of age; pediatric subgroup of <6y and 6 to <12y; and subgroup of 12-<18y and  $\geq$ 18y if applicable).

Individual pharmacokinetic parameters, as well as FVIII levels, will be displayed in subject listings.

### 6.4 Safety

All safety analyses will be performed on the safety analysis set for overall and by age groups respectively.

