#### 9.2.2 Sample Size Determination in Part B (PUPs/MTPs)

To fulfill the post-approval commitment enforced for KOVALTRY, the Sponsor is committed to collecting additional efficacy and safety data in previously untreated Chinese severe hemophilia A patients, in line with the CDE Technical Guideline on the Clinical Investigation of Recombinant Human Coagulation Factor VIII.

It is considered feasible to enroll approximately 6 PUPs/MTPs in Part B of this study.

Part B of this study is designed in accordance with the multinational clinical trial of KOVALTRY in previously untreated/minimally treated patients, LEOPOLD Kids Part B, where the annualized number of bleeds that occur within 48 hours after a prophylaxis infusion was the primary efficacy endpoint.

A mean of 1.9 (standard deviation 3.3) was observed for this ABR in LEOPOLD Kids Part B. Assuming the same distribution, the point estimate for the ABR within 48 hours after a prophylaxis infusion of 6 patients will be smaller than 2.9 with a probability of more than 80% (based on simulations of data for 6 patients from a negative binomial distribution).

In addition, in the SIPPET study (a multinational, prospective, randomized trial that assessed the incidence of FVIII inhibitors among PUPs treated with plasma-derived FVIII

containing von Willebrand factor or rFVIII products), the incidence of inhibitor development for the class of rFVIII products was 44.5% (95% CI: 34.7% to 54.3%).

Therefore, the true inhibitor rate for PUPs/MTPs is assumed to be within the range of 35% to 54%. With a sample size of 6 PUPs/MTPs, there is at least 92% power to observe at least 1 participant developing an inhibitor if the rate is between 35% and 54%. In case an event of inhibitor development is not observed, this sample size would provide more than 90% reassurance that the inhibitor rate should be no more than 35%.

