## Statistical Analysis Plan

BAY 81-8973 (KOVALTRY) / 19855

Page: 7 of 15

Willebrand factor or rFVIII products), the incidence of inhibitor development for the class of rFVIII products was 44.5% (95% CI: 34.7% to 54.3%).

Therefore, the true inhibitor rate for PUPs/MTPs is assumed to be within the range of 35% to 54%. With a sample size of 6 PUPs/MTPs, there is at least 92% power to observe at least 1 participant developing an inhibitor if the rate is between 35% and 54%. In case an event of inhibitor development is not observed, this sample size would provide more than 90% reassurance that the inhibitor rate should be no more than 35%.

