### **4.4 Interim Analyses and Data Monitoring**

In case the study will not be completed at the time of next renewal application, the most current results will be delivered for license renewal, and an interim analysis will be performed with all available data.

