### **Safety analysis set (SAF)**

Participants enrolled into the study and received at least 1 dose of study drug will be included in the SAF. The safety population will be used for the safety analysis.

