### 6.4.3 Adverse Events of Special Interest (AESI)

The adverse events of special interest in this study are:

- *Development of factor VIII inhibitors.*

Inhibitor development as measured by Nijmegen-modified Bethesda assay will be summarized by time point and presented in participant listings. The purpose of the listing is to delineate the clinical factors which may be positively associated with development of the inhibitor. Confirmation of the first positive inhibitor titer ( $\geq 0.6$  BU/mL) which is developed during the treatment with study drug will require repeat measurement of a second different sample. If the repeated inhibitor result is  $< 0.6$  BU/mL without intervention, the inhibitor is not confirmed and should not be reported as an SAE.

Inhibitors will be classified as being either low titer ( $\geq 0.6$  BU/mL and  $\leq 5$  BU/mL) or high titer based upon persistence of an inhibitor  $> 5$  BU/mL. Proportions of participants with inhibitor will be presented in an overview table. Exact Clopper Pearson CI for the proportion will be given if any inhibitor exists.

- *Hypersensitivity and allergic reactions including skin related and systemic reactions, such as anaphylactic reactions, (seriousness should be a case by case decision)*

The incidence of AEs, and AESI will be summarized and described for each age group and also for the overall study population combined.

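### In Part B the inhibitor proportion counts every child with one dose, so inhibitor-free children at few exposure days pull it down, and the over-90% assurance needs all six children at full risk

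*SAP*

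**What the plan says.** SAP 6.4 fixes the population: "All safety analyses will be performed on the safety analysis set for overall and by age groups respectively". SAP 5.1 defines that set: "Participants enrolled into the study and received at least 1 dose of study drug will be included in the SAF". SAP 6.4.3 then gives the estimator, "Proportions of participants with inhibitor will be presented in an overview table", and its interval, "Exact Clopper Pearson CI for the proportion will be given if any inhibitor exists". Protocol 9.4.4 agrees.

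Neither document sets a minimum number of ED or requires a post-dose inhibitor test for the denominator, and neither plans an incidence by ED. The dropout rule in SAP 4.2 covers the bleeding rate and a listing. The only set with a 50-ED condition is the per-protocol set, which is for Part A efficacy. The Protocol synopsis aims for about six evaluable Part B children but does not define evaluable.

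If the study is unfinished at licence renewal, SAP 4.4 says "an interim analysis will be performed with all available data", with no ED cut-off.

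The sample-size text (Protocol 9.2.2, SAP 3.1.2) makes two claims: "With a sample size of 6 PUPs/MTPs, there is at least 92% power to observe at least 1 participant developing an inhibitor" for a true rate of 35% to 54%, and, if none is seen, "this sample size would provide more than 90% reassurance that the inhibitor rate should be no more than 35" per cent.

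**The concern.** The quantity of interest in Part B is the chance of an inhibitor over the planned course of at least 50 ED. Protocol 6.6.2 treats the first exposures as potentially critical and requires testing every 3 to 5 ED up to 20 ED. A child who stops without an inhibitor at a low ED tells us about risk up to that point only, yet adds a full unit to the denominator. Children who leave because of an inhibitor count as events, so the distortion comes only from inhibitor-free children at low ED, and it runs downward.

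Such children are plausible. Prophylaxis may start once weekly, so a child eight weeks in could have about 8 ED, and Protocol 7.2.8 expects most children to need 6 to 12 months to reach 50. With six children, one or two denominators change the message. The sample-size claim has the same weakness: it takes six children at full risk for granted, and nothing in the planned denominator secures that.

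**Working it through.** **Inputs.** Six children and a true rate p of 35% to 54% come from Protocol 9.2.2 and SAP 3.1.2. Two quantities are not in the documents and are assumed: m, the number of the six who are under-exposed (0 to 3), and s, the share of the cumulative hazard that such a child has passed (0 to 0.5, and 0.8 in step 5).

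**1. The plan's own figures.** The chance of at least one inhibitor is 1 − (1 − p)^6. At p = 0.35 this is 1 − 0.65^6 = 1 − 0.0754 = 92.5%; at p = 0.54 it is 99.1%. With zero events the one-sided 90% upper bound is 1 − 0.1^(1/6) = 31.9%, below 35%. Both claims reproduce.

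**2. Under-exposed children.** An under-exposed child contributes s of a full child, so at p = 0.35 the assurance is 1 − 0.65^(6 − m + m·s).

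| m | s = 0 | s = 0.5 | 90% upper bound at zero events, s = 0 |
|---|---|---|---|
| 0 | 92.5% | 92.5% | 31.9% |
| 1 | 88.4% | 90.6% | 36.9% |
| 2 | 82.1% | 88.4% | 43.8% |
| 3 | 72.5% | 85.6% | 53.6% |

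**3. Expected safety-set proportion.** This is [(6 − m)p + m(1 − (1 − p)^s)]/6. The ranges run from s = 0 to s = 0.5.

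| m | True rate 35% | True rate 54% |
|---|---|---|
| 1 | 29.2% to 32.4% | 45.0% to 50.4% |
| 2 | 23.3% to 29.8% | 36.0% to 46.7% |
| 3 | 17.5% to 27.2% | 27.0% to 43.1% |

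**4. What an ED-based incidence would do.** Take two inhibitors, two inhibitor-free early leavers and two children who complete. The safety-set figure is 2/6 = 33.3% whatever the timing. A Kaplan-Meier-type figure depends on when the two leave:

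- before either inhibitor: 2/4 = 50.0%;
- between the two: 1 − (5/6)(2/3) = 44.4%;
- after both: 1 − (5/6)(4/5) = 33.3%.

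If nobody leaves early, it equals the plain proportion.

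**5. A 50-ED evaluable ratio as the alternative.** Divide all confirmed inhibitors by (confirmed inhibitors plus negatives at 50 ED or more). Take p = 0.35 and m = 2. With X inhibitors among the four fully followed children and Y among the other two, the ratio is (X + Y)/(4 + Y), where X is binomial(4, 0.35) and Y is binomial(2, 1 − 0.65^s).

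- s = 0.5: the ratio averages 39.9%, the safety-set proportion 29.8%.
- s = 0.8: the ratio averages 42.2% (7.2 points too high), the safety-set proportion 33.1% (1.9 points too low).

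**The case against.** The plan is not silent on exposure. SAP 6.4.3 says "Inhibitor development as measured by Nijmegen-modified Bethesda assay will be summarized by time point and presented in participant listings", and the Part B visits are set by ED (Protocol 8.10.2). SAP 4.1 reports numbers available and missing, SAP 6.1.2 summarises exposure days, and Protocol 6.8.1 gives early leavers the final-visit investigations, which include an inhibitor test. With about six children, a careful reader could reconstruct who was tested at which ED. This stands as mitigation. It does not change the headline proportion or its interval, and a negative exit test at a low ED says nothing about later exposure.

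The study is descriptive and the assurance is a planning statement; no section says it will be attached to results. The interim is conditional. Both points stand and limit the consequence.

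A reader might infer several stronger things that the documents do not support:

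- **The plan classes a low-ED child as a completed negative.** No section says so; such a child simply stays in the denominator.
- **The assurance falls to 82.1% or 72.5%.** Those figures need two or three of six children with no accrued risk at all. One child at half the risk leaves 90.6%, so the claim survives.
- **The main estimate should be the 50-ED ratio.** It counts inhibitors at any ED but negatives only at 50 ED or more, so it errs upward (step 5). With six children at about 25 ED it would read 1/1 after one inhibitor and 0/0 after none.
- **The same rule should apply in Part A.** Twice-weekly dosing for 26 weeks gives about 52 infusions, and the package insert (Protocol 12) reports 37 to 103 ED in children treated for at least six months. A 50-ED cut could drop Part A completers.
- **Six or 50 ED marks a defined risk period, or inhibitors outrank other safety endpoints.** The documents define no risk period and do not rank inhibitors above adverse events. The nearest anchors are 20 ED (end of frequent testing) and 50 ED (treatment target).

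**Conclusion.** The point holds for Part B. Measured against incidence over the planned exposure, the one-dose denominator lets inhibitor-free children at low ED bias the proportion downward. At a true rate of 35%, one such child lowers the expected figure to between 29.2% and 32.4%, and two lower it to between 23.3% and 29.8%. The sample-size arithmetic is correct, but its over-90% claim depends on follow-up: it fails if one child has accrued no risk and survives, narrowly, if that child has passed half.

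These sizes rest on assumed values of m and s, because no Part B dropout rate is given. If all six reach 50 ED or develop an inhibitor, there is no bias. A related gap is that no interval is planned when no inhibitor occurs, which is the case the assurance addresses; the two-sided 95% upper limit for 0/6 is 1 − 0.025^(1/6) = 45.9%.

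**What to change.** For Part B only:

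1. Keep the safety-set proportion in SAP 6.4.3.
2. Beside it, for the final analysis and for the interim if run, add a cumulative inhibitor incidence by ED (Kaplan-Meier type), censoring inhibitor-free children at the ED of their last negative test, with numbers at risk at 20 and 50 ED.
3. List ED at last negative test for each child.
4. The ratio of confirmed inhibitors to (confirmed inhibitors plus negatives at 50 ED or more) may be shown as a supplementary upper-side figure, with a note that it can err upward and is uninformative when few children have reached 50 ED.
5. State in Protocol 9.2.2 and SAP 3.1.2 that the 92% and over-90% figures assume six children followed through 50 ED or to an inhibitor.

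The cost is wording, one extra table, and wider, less favourable bounds. Exposure days and inhibitor results are already collected. The SAP still rests on protocol version 2.0 while the protocol is at 4.0, so the change can go into an update. With six children the curve will be coarse, which is why the numbers at risk must be shown with it.
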